#### **5.4. Prior and Concomitant Medications**

Subjects who have not had a bilateral orchiectomy must be receiving androgen deprivation therapy with a GnRH analogue prior to enrollment and must continue on GnRH-analogue therapy for the duration of the study.

Abiraterone and chemotherapy are prohibited while on study drug.

Phase 1b Monotherapy: Subjects must have previously received abiraterone and/or enzalutamide.

Phase 2 Monotherapy Dose Expansion (Group 1): Subjects must have previously received enzalutamide. Subjects must not have previously received chemotherapy for mCRPC.

Phase 1b Combination Therapy Dose Escalation and Phase 2 Combination Dose Expansion (Group 2): Subjects must have previously received abiraterone, but must not have previously received enzalutamide or chemotherapy for mCRPC.

Phase 2 Combination Therapy Dose Expansion (Group 3): Subjects must have previously received enzalutamide and have been on continuous enzalutamide for the 12 weeks prior to Cycle 1, Day 1. Subjects must not have previously received chemotherapy for mCRPC. Subjects must not have previously received chemotherapy for mCRPC.

In vitro data indicate GS-5829 is a substrate of CYP3A4. Co-administration of CYP3A4 inhibitors may increase GS-5829 exposure. As such, co-administration of moderate and strong CYP3A4 inhibitors with study drug is prohibited in this study.

Co-administration of CYP3A4 inducers may decrease GS-5829 exposure. As such, moderate and potent CYP3A4 inducers are prohibited while subject is on study drug and  $\geq$  2 weeks prior to study drug administration except for subjects in Group 2 who may receive enzalutamide as described in the protocol. Examples of moderate and strong CYP3A4 inhibitors and inducers are provided in the table below.

**Table 5-3. Examples of Concomitant Medications Prohibited in this Study**

	Moderate	Strong
CYP3A4 Inhibitor	Aprepitant, ciprofloxacin, crizotinib, diltiazem, erythromycin, fluconazole, imatinib, verapamil	Clarithromycin, conivaptan, grapefruit juice, itraconazole, ketoconazole, nefazodone, posaconazole, telithromycin, voriconazole
CYP3A4 Inducer	bosentan, modafinil, nafcillin	carbamazepine, phenytoin, rifampin, St. John's wort

Toxicology data from dogs demonstrated minimal to moderate gastrointestinal, pulmonary, muscular and intracardiac bleeding. The mechanism for the bleeding is not understood. Anticoagulant medications are prohibited on study; this includes vitamin K antagonists (eg, warfarin), low molecular weight heparin, Factor Xa inhibitors, thrombin inhibitors and aspirin. If anticoagulation therapy needs to be initiated while on study treatment, the Investigator should consult with the Medical Monitor to determine if study treatment should be discontinued.

For subjects receiving enzalutamide, CYP3A4, CYP2C9, and CYP2C19 substrates with a narrow therapeutic index should be avoided with the exception of study drug, as enzalutamide may decrease the plasma exposures of these drugs. Additional INR monitoring should be conducted in subjects receiving warfarin and enzalutamide. Strong or moderate CYP3A4 or CYP2C8 inducers and strong CYP2C8 inhibitors should be avoided. Refer to the prescribing information for XTANDI® for more information regarding potential drug interactions.

## **5.5. Accountability for GS-5829 and Enzalutamide**

The investigator is responsible for ensuring adequate accountability of all used and unused study drug. This includes acknowledgement of receipt of each shipment of study drug (quantity and condition). All used and unused study drug dispensed to subjects must be returned to the site.

Accountability records will be provided to each study site to:

- Record the date received and quantity of study drug kits
- Record the date, subject number, subject initials, the study drug kit number dispensed
- Record the date, quantity of used and unused study drug returned, along with the initials of the person recording the information.

### **5.5.1. GS-5829 and Enzalutamide Return or Disposal**

Study drug should be retrieved from each subject at the end of each dispensing interval. The quantity of study drug and the date returned by the subject should be recorded in the study drug accountability records. All study drug returned by the subject should be retained for review by the study site monitor prior to destruction.

Please see Section [9.1.7](#) for more information.

## **6. STUDY PROCEDURES**

The study procedures to be conducted for each subject enrolled in the study are presented in tabular form in [Appendix 2](#) and [Appendix 3](#) and described in the text below. Additional information is provided in the study manual.

The investigator must document any deviation from protocol procedures and notify the sponsor or contract research organization (CRO).

Safety and tolerability assessments will include regular monitoring of AEs, changes from baseline in laboratory variables, physical examinations, vital signs, and special safety assessments like ECGs.

From the time of obtaining informed consent through the first administration of investigational medicinal product, record all serious adverse events (SAEs), as well as any non-serious AEs related to protocol-mandated procedures on the AEs electronic case report form (eCRF). All other untoward medical occurrences observed during the Screening period, including exacerbation or changes in medical history are to be captured on the medical history eCRF. See Section [7](#) for additional details.

### **6.1. Subject Enrollment and Treatment Assignment**

Subjects will be assigned a unique screening number at the time of consent. Subject eligibility will be established at the conclusion of the screening evaluations. Once eligibility is confirmed, subjects will be assigned a unique subject number. The screening number and/or subject ID will be assigned for that individual subject by Gilead. The investigator will submit an enrollment form to Gilead for review and approval prior to enrollment of the subject.

It is the responsibility of the investigator to ensure that each subject is eligible for the study before start of treatment.

### **6.2. Study Procedure Descriptions**

The sections below describe the individual study procedures outlined in the subsequent sections and the Study Procedures Table. During the treatment period, all visits may be performed within the specified window for that study visit.

#### **6.2.1. Informed Consent**

All subjects must sign and date the most recent IRB/IEC-approved informed consent form before any study procedures are performed. **CCI**

Subjects who screen fail must re-sign the informed consent, in the event any screening procedures will be performed outside of the 28-day screening window from the time of the first informed consent.

#### **6.2.2. Medical History**

A complete medical history will be obtained by the Investigator or qualified designee prior to enrollment and recorded on the eCRF.

#### **6.2.3. Prior and Concomitant Medications**

At Screening, all medications taken up to 30 days prior to the screening visit will be recorded on the eCRF. In addition, supportive therapies given during the course of the study (e.g. blood transfusion, growth factor) should be collected and recorded on the eCRF.

At each study visit, the site will capture any and all medications taken by the subject since the last visit or during the visit (as applicable). Concomitant medications include prescription and non-prescription medications, pre-infusion medications (e.g. anti-emetics), and vitamins and minerals.

#### **6.2.4. Physical Examination**

The Investigator or qualified designee will perform a complete physical examination at Screening and at the End of Treatment visit. Pre-dose abnormal findings will be reported on the medical history page of the eCRF. Any changes from the pre-dose baseline physical examination that represent a clinically significant deterioration will be documented on the AE page of the eCRF.

Weight (without shoes) should be measured with each physical examination.

Height (without shoes) should be measured at Screening only.

Beginning at C1D1, a modified physical examination will be performed to monitor for any changes, and will also include weight and assessment of disease-related clinical signs and symptoms.

## **6.2.5. Vital Signs**

Vital signs will include blood pressure, respiratory rate, pulse, oxygen saturation and temperature. All measurements will be recorded on the appropriate eCRF page with appropriate source documentation. Any abnormal measurements may be repeated and reported as AEs if appropriate. All measures of blood pressure will be performed using standard sphygmomanometry. Measurements of blood pressure should be taken per institutional guidelines.

## **6.2.6. Electrocardiogram**

TriPLICATE 12-lead ECGs reporting ventricular rate, PR, QRS, QT, and QTc intervals will be obtained at the applicable study visits and transferred to a central vendor for storage. ECGs should always be collected prior to PK (or any other blood draw) if they are to be collected at the same nominal time point. Subjects should be resting quietly and free of distraction (e.g. tv, conversation) for 10 minutes prior to ECG collection and ECGs should be collected over a 5 minute window at each time point.

The Investigator or qualified designee will review all ECGs. The ECG tracings will be maintained in the source documentation of each subject and the appropriate data reported on the eCRF.

## **6.2.7. ECOG Performance Status**

The Eastern Cooperative Oncology Group (ECOG) Performance Status is an investigator assessment of the impact of the disease on the subject's activities of daily living. ECOG will be scored using the scale index in [Appendix 8](#).

## **6.2.8. Adverse Events**

Subjects will be assessed for adverse events (AEs) per guidelines in the National Cancer Institute (NCI) CTCAE (version 4.03) at the time points outlined in [Appendix 2](#) and [Appendix 3](#). Any AEs reported after informed consent is obtained and throughout the study will be recorded on the eCRF with appropriate source documentation. The subject will be assessed for AEs approximately 30 days after the last dose of study drug. Please refer to [Appendix 6](#) for CTCAE grading criteria.

Please refer to Section [7](#) for additional information on AE reporting.

## **6.2.9. Disease Assessments**

### **6.2.9.1. Bone Scans**

Subjects will undergo radionuclide bone scan at Screening [within 8 weeks before Cycle 1 Day 1 (or Study Day 1 if in the combination therapy) if the scan was performed as part of standard medical practice] and every 12 weeks during the treatment period. Scans at the End of Treatment visit are not necessary if the prior scan was performed within 4 weeks prior to the EOT visit date.

#### 6.2.9.2. CT or MRI

Subjects will be assessed by CT scan with contrast (or MRI, if unable to tolerate CT contrast) of the chest, abdomen and pelvis to document metastatic disease, identify target lesions and to assess response as per PCWG2 guidelines.

In subjects who cannot tolerate iodinated contrast, a CT of the lung without contrast and MRI of the abdomen should be performed. Imaging by CT scan (with contrast) or MRI or applicable scan will be performed at Screening (within 8 weeks before Cycle 1 Day 1 if the scan was performed as part of standard medical practice) and every 12 weeks during the treatment period regardless of cycle number or dose interruption. During the treatment, scans may be performed at time points other than 12 weeks, as clinically indicated, to assess tumor progression.

Tumor burden will be characterized at baseline and subsequent response assessments will be carried out according to the PCWG2 Criteria. The same radiographic procedure and specification (eg, the same contrast agent, slice thickness, etc.) used to define measurable lesions at baseline must be used throughout the study for each subject.

Please refer to [Appendix 5](#) for additional information on PCWG2 study progression criteria.

#### 6.2.10. Laboratory Assessments

Screening laboratory samples should be obtained within 28 days prior to Study Day 1/Cycle 1 Day 1 dose (GS-5829). Local laboratory CBC assessments may be collected as required for dose adjustments throughout the study. Local laboratory assessments resulting in a dose change will be reported on the eCRF.

The central laboratory will be responsible for chemistry, hematology, coagulation, and urinalysis testing per [Table 6-1](#) and storage of other study samples. If central laboratory results are not available, local laboratories may be used for dosing decision. Other tests listed in [Table 6-1](#) will be performed by Gilead or a designated laboratory. Any sample collected per the Schedule of Assessments ([Appendix 2](#) and [Appendix 3](#)) may be analyzed for any tests necessary to ensure subject safety. Specific instructions for processing, labeling, and shipping samples will be provided in the central laboratory manual. The date and time of sample collection will be recorded in the subject's source documentation and reported to the central laboratory.

The date and time of previous GS-5829 dose will be recorded in the subject's source documentation on days where PK is collected. White blood cell (WBC) differentials will be reported as absolute counts. All laboratory tests must be reviewed for clinical significance by the Investigator or qualified designee. Eligibility will be based on central laboratory assessments and will be collected within 7 days of Study Day 1/C1D1.

Study Day 1 and/or Cycle 1 Day 1 pre-dose samples may be drawn up to 2 days prior to the visit.

The analytes listed in [Table 6-1](#) will be tested.

**Table 6-1. Analytes**

Serum Chemistry	Hematology	Other
Sodium Potassium Chloride Glucose BUN Creatinine Creatinine Clearance a ALT AST Alkaline phosphatase Total bilirubin b Total protein Albumin Calcium Magnesium Phosphate AAG	White Blood Cell (WBC) Count Hemoglobin Hematocrit Platelet Count Neutrophils (ANC) Lymphocytes Monocytes Basophils Eosinophils	GS-5829 concentration Concentrations of GS-5829 metabolite(s), enzalutamide and enzalutamide metabolites, as applicable, may be determined Serum and Plasma CCI Hepatitis B surface antigen Hepatitis C antibody PSA Total testosterone
	Coagulation	
	PT/INR aPTT Fibrinogen Factor VII Fibrinogen Depredation Products	
	Urine	
	Urinalysis	

a Cockcroft-Gault using Actual Body Weight: CRCL (mL/min) = [(140-age(years)) \* weight(kg)] / (serum creatinine (mg/dL)\*72)

b Includes direct bilirubin

c At Screening only

### **6.2.11. Pharmacokinetic & Pharmacodynamic Samples**

PK samples will be collected at the timepoints listed below. GS-5829 plasma concentrations will be determined using a validated assay. Plasma concentrations of GS-5829 metabolites and/or enzalutamide and/or enzalutamide metabolites may be determined. Plasma protein binding of analytes may be evaluated. PD samples may be modified based on the emerging data.

#### **Phase 1b Dose Escalation:**

##### **Monotherapy Dose Escalation**

PK and PD samples for GS-5829 will be collected on Day 8 of Cycle 1 at pre-dose, 0.5, 1, 2, 3, 4, 6, 8, and 24 hours post-dose, as well as pre-dose and 1-4 hours after GS-5829 administration on Day 1 and Day 15 of Cycle 1 and anytime on Day 1 of Cycles 2 through 6.

At one or more dose levels, PK samples may be collected on Day 1 of Cycle 2 at pre-dose and 0.5, 1, 2, 3, 4, 6, 8, and 24 hours post-dose after GS-5829 has been administered in the fed state. If evaluation of food effect cannot be performed on Cycle 2, Day 1, it may be performed at a visit after Cycle 2, Day 1, if necessary.

## **Dose Escalation with Enzalutamide**

PK and PD samples for GS-5829 will be collected on Day 1 and Day 15 of Cycle 1 at pre-dose 0.5, 1, 2, 3, 4, 6, 8 and 24 hours post-dose and anytime on Day 1 of Cycles 2 through 6.

### **Phase 2 Dose Expansion:**

#### **Group 1**

PK and PD samples will be collected on Day 8 of Cycle 1 at pre-dose and 1, 2, 4, and 6 hours post-dose. Sparse PK and PD samples will be collected at pre-dose and 1 - 4 hours post-dose on Cycle 1 Day 1 and Day 15 and anytime on Day 1 of Cycles 2 through 6. PK samples may be collected on Day 1 of Cycle 2 at pre-dose and 1, 2, 4, and 6 hours post-dose after GS-5829 has been administered in the fed state. If evaluation of food effect cannot be performed on Cycle 2, Day 1, it may be performed at a visit after Cycle 2, Day 1 if necessary.

#### **Group 2**

PK and PD samples will be collected on Cycle 2, Day 1 at pre-dose and 1, 2, 4, and 6 hours post-dose. Sparse PK and PD samples will be collected at pre-dose and 1 - 4 hours post-dose on Cycle 1, Day 1 and Day 15 and anytime on Day 1 of Cycles 3 through 6.

#### **Group 3**

PK and PD samples will be collected on Cycle 2, Day 1 at pre-dose and 1, 2, 4, and 6 hours post-dose. Sparse PK and PD samples will be collected at pre-dose and 1 - 4 hours post-dose on Cycle 1, Day 1 and Day 15 and anytime on Day 1 of Cycles 3 through 6.

### **6.3. Biomarker Testing**

#### **6.3.1. Biomarker Samples to Address the Study Objectives**

Biological specimens detailed below will be collected in this study and will be used to evaluate the association of exploratory systemic and/or tissue specific biomarkers with study drug response, including efficacy and/or adverse events and to increase knowledge and understanding of the biology of disease and/or the validation of a companion diagnostic for GS-5829. The specific analyses will include, but will not be limited to, the biomarkers and assays listed below. Since biomarker science is a rapidly evolving area of investigation, and adverse events in particular are difficult to predict, it is not possible to specify prospectively all tests that will be done on the specimens provided. The testing outlined below is based upon the current state of scientific knowledge. It may be modified during or after the end of the study to remove tests no longer indicated and/or to add new tests relevant to the study objectives based upon the growing state of art knowledge.

Whole blood, plasma and serum biomarkers will be collected in this study as detailed in Section 6.3.1.2 and will be used to evaluate the association of exploratory systemic and/or tissue specific biomarkers with study drug response, including efficacy and/or AEs and to increase knowledge and understanding of the biology of prostate cancer or related diseases.

Biomarker specimens will be collected from all subjects. In addition, sampling time points may be eliminated based upon emerging data.

The biomarker samples will be destroyed no later than 10 years after the end of study CCI [REDACTED]

For sampling procedures, storage conditions, and shipment instructions, see the Sample Handling and Logistics Manual.

#### 6.3.1.1. Archival Tumor Tissue

Paraffin embedded blocks from archival tumor tissue or freshly cut unstained slides will be requested for all subjects who have tissue available. This is not an optional part of the study and samples should be collected from all participating subjects with available tissue. Efforts to acquire a tissue sample should begin on Day 1. The samples will be used to evaluate the association of exploratory biomarkers with study drug response and may include protein, somatic (tumor-specific) DNA and gene expression analysis.

#### 6.3.1.2. Serum, Plasma and Whole Blood Biomarkers

Whole blood for PD biomarkers will be collected at the time points listed in [Appendix 2](#) and [Appendix 3](#). Serum collected for PSA will also be assessed. Whole blood and plasma for Circulating Tumor Cells (CTCs), exosome, circulating proteins and circulating tumor DNA may also be collected to evaluate for the presence of AR-V7 variant and for other exploratory biomarker analysis. In addition, any remaining plasma samples obtained to measure GS-5829 levels may also be used to measure the exploratory PD biomarkers described above.

[figure not shown]
CCI [REDACTED]

[REDACTED]

CCI [REDACTED]

[REDACTED]

CCI

CCI

CCI

#### **6.4. Pretreatment Assessments**

##### **6.4.1. Screening Visit**

The screening date will be defined as the date the subject signs the informed consent. Subjects will be screened within 28 days of enrollment to determine eligibility for participation in the study. Screening laboratory results for chemistry, hematology, coagulation and urinalysis should be obtained from central laboratory. Subjects must meet all eligibility criteria in order to be enrolled. Subjects who do not enroll within the 28 day screening window will be screen failed. Re-screening is allowed (see Section 6.2.1).

The following will be performed and documented during Screening:

- Obtain written informed consent
- Obtain medical history, including prior/concomitant medication review
- Complete physical examination including body weight and height
- Vital Signs
- Triplicate 12-lead ECG
- ECOG Performance Status

- Laboratory assessments
  - Chemistry
  - Complete blood count (CBC) with differential
  - Total testosterone
  - Coagulation
  - Urinalysis
- Bone Scan
- CT scan with contrast or MRI (scans taken as part of standard medical practice up to 8 weeks prior to C1D1 are acceptable)

■

- Record any adverse events (occurring after signing of the consent form)
- Complete subject/visit information on enrollment form

Subjects meeting all of the inclusion criteria and none of the exclusion criteria, as approved by Gilead, will return to the clinic within 28 days after screening for enrollment into the study.

From the time of obtaining informed consent through the Cycle 1 Day 1 dose, record all serious adverse events (SAEs), as well as any adverse events related to protocol-mandated procedures on the AE eCRF. All other untoward medical occurrences observed during the screening period, including exacerbation or changes in medical history are to be captured on the medical history eCRF. See Section 7 Adverse Events and Toxicity Management for additional details.

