### **5.3. Dosage and Administration of GS-5829 and Enzalutamide**

GS-5829 tablets will be provided by Gilead Sciences, Inc. and will be taken orally. Initiation of treatment with the study drug will take place after enrollment and cohort assignment. Subjects will take their dose of study drug at approximately 24-hour intervals. To reduce inter-subject variability on efficacy and safety, subjects will be instructed to take GS-5829 approximately 1 hour before or 2 hours after a meal, unless otherwise specified by protocol. Grapefruit juice is prohibited while on study drug. In one or more monotherapy dose levels or in the monotherapy expansion (Group 1), on Day 1 of Cycle 2, approximately 10 subjects may be asked to administer GS-5829 in fed state with a standardized meal (~500 to 600 calories and ~30% of calories from fat). If evaluation of food effect cannot be performed on Cycle 2, Day 1, it may be performed at a visit after Cycle 2, Day 1 (where subject has taken at least 7 consecutive days of GS-5829), if necessary.

XTANDI® (enzalutamide) will be supplied as 40 mg capsules for oral administration. Subjects assigned to receive enzalutamide in combination with GS-5829 in this study will orally self-administer 4 capsules of enzalutamide (160 mg total daily dose) once daily at approximately 24-hour intervals beginning on Study Day 1 and GS-5829 will start, at the assigned dose, 14 days ( $\pm$  3 day window) later on Cycle 1 Day 1. Subjects enrolled into Group 3 should be on at least 12 weeks of continuous enzalutamide treatment prior to starting Cycle 1 Day 1. Capsules should be swallowed whole and may be taken with or without food. Refer to [Appendix 9](#) for further details.

If the subject misses a dose, he should be instructed to take the study drug as soon as he remembers, unless more than 8 hours have elapsed since the scheduled time of the missed dose. In this case, the subject should be instructed to wait and take the next dose at the regularly scheduled time. Subjects should not take more than 1 dose of study drug at a time.

If a subject vomits within 5 minutes of dosing and the tablet is visible, the subject should be instructed to re-dose. If a subject vomits more than 5 minutes after dosing or if the tablet is not visible, the subject should be instructed to wait and take the next dose at the regularly scheduled time.

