### **6.5.2. Baseline Visit / Cycle 1 Day 1 (C1D1)**

Subjects in a monotherapy treatment who have met all eligibility criteria will return to the clinic on C1D1 to perform baseline assessments. C1D1 is defined as the date of the first dose of GS-5829, and may occur within 3 days following enrollment.

The following baseline assessments will be conducted prior to the first dose of GS-5829:

- Physical examination, including weight
- Vital signs, within 15 minutes prior to the GS-5829 dose
- Triplicate 12-lead ECG
- ECOG performance status

- Laboratory assessments and blood sampling (refer to [Table 6-1](#))
  - Chemistry
  - CBC with differential
  - Coagulation
  - Request archival tumor tissue specimen: Efforts to acquire tissue sample should begin on C1D1 for all subjects
  - Urinalysis
  - GS-5829 PK (see [Appendix 2](#) and [Appendix 3](#))
  - Pharmacodynamics (see [Appendix 2](#) and [Appendix 3](#))
  - PSA
- Record any adverse events
- Concomitant medications review
- IP accountability and dispensing of IP and Dosing Diary.

The site will train the subject on the dosing schedule for the IP and the Dosing Diary at the time of dispensing.

The following assessments will be conducted after the first dose of GS-5829:

- Triplicate ECG (see [Appendix 2](#) and [Appendix 3](#))
- Vital signs (2 and 4 hours post GS-5829 dose [ $\pm 15$  minutes])
- GS-5829 PK (see [Appendix 2](#) and [Appendix 3](#))
- Pharmacodynamics (see [Appendix 2](#) and [Appendix 3](#))

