#### **7.3.2. Adverse Events**

Following the initiation of study medication, all AEs (regardless of cause or relationship) until 30 days after last administration of study drug, must be reported to the eCRF database as instructed.

All AEs should be followed up until resolution or until the AE is stable, if possible. Gilead Sciences may request that certain AEs be followed beyond the protocol defined follow up period.

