7.1.5. Treatment-Emergent Adverse Events

7.1.5.1. Definition of Treatment-Emergent Adverse Events

Treatment-emergent adverse events (TEAEs) are defined as 1 or both of the following:

- Any AEs with an onset date on or after the study drug start date and no later than 30 days after permanent discontinuation of study drug
- Any AEs leading to premature discontinuation of study drug.

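### Protocol 6.4.1 restricts AE recording until the first GS-5829 dose, contradicting Sections 6 and 7.3, so non-serious AEs in the enzalutamide lead-in may be under-recorded

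*Protocol*

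**What the plan says.** Protocol Section 6.4.1 gives the rule "From the time of obtaining informed consent through the Cycle 1 Day 1 dose, record all serious adverse events (SAEs" and adds only AEs related to protocol-mandated procedures. It sends to medical history "All other untoward medical occurrences observed during the screening period". The same section's task list also says "Record any adverse events (occurring after signing of the consent form", and it refers to Section 7 for details.

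The introduction to Protocol Section 6 has nearly the same rule with a different end point: "From the time of obtaining informed consent through the first administration of investigational medicinal product". Section 7.3.1 applies the restriction only before study medication starts. Section 7.3.2 then requires full reporting: "Following the initiation of study medication, all AEs (regardless of cause or relationship) until 30 days after last administration of study drug".

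The two end points differ when enzalutamide comes first. Section 6.5.2 states that "C1D1 is defined as the date of the first dose of GS-5829". Section 5.3 has combination subjects take enzalutamide "once daily at approximately 24-hour intervals beginning on Study Day 1 and GS-5829 will start, at the assigned dose, 14 days" later, with a window of 3 days either way.

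SAP Section 3.1.2 defines study drug as GS-5829 or enzalutamide. SAP Section 7.1.5.1 counts as treatment-emergent "Any AEs with an onset date on or after the study drug start date". SAP Section 7.1.6.1 summarises these events by treatment group.

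**The concern.** For monotherapy subjects the first GS-5829 dose is the first study drug dose, so the two rules agree. For subjects with an enzalutamide lead-in they disagree for about two weeks of active treatment. In that interval Section 6.4.1 asks only for SAEs and procedure-related AEs, while Section 7.3.2 asks for everything.

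Safety and tolerability of the combination is a primary Phase 1b objective. Section 1.5 lists fatigue, hypertension, hot flushes and diarrhea among the known toxicities of enzalutamide, so non-serious lead-in events are plausible. If a site left such an event off the AE form, it would be missing from every TEAE table. If the site entered it as general medical history, SAP Section 5.3 would leave it uncoded and only listed.

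The SAP raises a second, smaller issue. Lead-in events that are captured appear under the assigned GS-5829 treatment group, with nothing to show that they began before GS-5829 did.

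**Working it through.** The documents give no figure to reproduce. The check sets the recording rules side by side and then measures the interval on which they differ.

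**Step 1. Where each text ends restricted recording**

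| Source | Restriction ends, or full recording starts | Lead-in AEs (non-serious, non-procedural) |
|---|---|---|
| Protocol 6.4.1, restricting sentence | Cycle 1 Day 1 dose | Not asked for |
| Protocol 6.4.1, task list | Consent | Recorded |
| Protocol 6, introduction | First dose of investigational product | Recorded |
| Protocol 7.3.1 and 7.3.2 | Start of study medication | Recorded |
| Protocol 6.2.8 | Consent | Recorded |
| Protocol Appendix 3, AE footnote | Consent | Recorded |
| SAP 7.1.5.1 with 3.1.2 | First dose of either drug | Counted as TEAEs |

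The Study Day 1 list (6.5.1) and the Cycle 1 Day 1 list (6.5.2) also call for any adverse events to be recorded.

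**Step 2. Does enzalutamide start the clock?** Yes. Protocol Section 5 handles it under investigational medicinal products, Section 5.3.1 names it with GS-5829 as study drug, and SAP Section 3.1.2 does the same. The start of study medication in a lead-in cohort is therefore Study Day 1.

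**Step 3. Who is affected?** The Phase 1b combination cohorts and Group 2. The design text in Section 3.2 has Group 3 continue enzalutamide it was already taking, with no new lead-in. An Appendix 3 footnote nevertheless lists Group 3 among those starting enzalutamide on Study Day 1, and the two places need to be reconciled. SAP Section 1 says that phase 2 will not proceed, so in practice the data at issue are from Phase 1b.

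**Step 4. Length of the disputed interval.** With a lead-in of L days and a first cycle of 28 days, its share of the time from Study Day 1 to Cycle 1 Day 28 is L/(L + 28).

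- L = 14: 14/42 = 33%
- L = 14 − 3 = 11: 11/39 = 28%
- L = 14 + 3 = 17: 17/45 = 38%

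The denominator is a choice made here for scale. The full TEAE window runs to 30 days after the last dose, so the share of that longer window is smaller.

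**Step 5. Where would an event go under 6.4.1 alone?** The synopsis places screening before first dosing on Study Day 1 or Cycle 1 Day 1, and Section 5.1 treats a subject as enrolled once treatment has started. A lead-in event is therefore not a screening event. Read strictly, 6.4.1 sends it to neither the AE form nor medical history. Read loosely, a site might put it in medical history.

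**Step 6. What is untouched?** Under Section 3.2 the safety review of combination cohorts follows 28 days after the first GS-5829 dose, and a DLT must be possibly related to GS-5829. SAP Section 3.1.4 also ties the DLT set to days on GS-5829. SAEs are recorded from consent under every rule.

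**The case against.** The strongest reply is that the protocol as a whole does require these events to be recorded. Section 7.3.2 is mandatory in tone and is the section to which 6.4.1 defers. Sections 6 and 6.2.8 and Appendix 3 agree with it. The restricting sentence sits under pretreatment assessments, and its medical-history route is limited to screening. This stands. A reader might infer from 6.4.1 that lead-in AEs are simply not captured, but the documents do not support that. They show one sentence out of line with the rest, and no evidence of what sites did.

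A reader might also infer that the comparison between dose levels is distorted whichever rule was followed. That is not shown either. Every Phase 1b combination cohort has the same planned lead-in, so captured events add background to all of them and favour no particular dose. Nor does it help to note that one subject moves a rate by 17 points in a cohort of six (1/6) or 33 points in a cohort of three (1/3). That is true of any misclassified subject and says nothing about how often it happened.

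Counting TEAEs from the first dose of either drug follows Protocol Section 8.6.2, so the lack of a split is an omission worth filling, not an error. The planned tables of TEAEs related to GS-5829 help only in part: SAP Section 7.1.3 describes a single question about relation to study treatment, and the tables of all TEAEs, Grade 3 or higher TEAEs and treatment-emergent SAEs have no such filter.

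Finally, SAP Section 1 reports that all Phase 1b subjects have stopped study drug and had their safety follow-up visit. Rewording the protocol now changes no collected data. That also stands, and it moves the weight of the fix to the query and the SAP.

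**Conclusion.** Section 6.4.1 contradicts Sections 6, 7.3.1 and 7.3.2 on when full AE recording begins. In lead-in cohorts the disagreement lasts 14 days (11 to 17), or 33% (28% to 38%) of the time from Study Day 1 to Cycle 1 Day 28. It could cause under-recording of non-serious, non-procedural AEs; it is not an established gap in collection. The actual loss cannot be sized, because the documents give neither a lead-in event rate nor the proportion of sites that followed 6.4.1.

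The conclusion rests on two readings, both supported by the text: enzalutamide is study medication, and Cycle 1 Day 1 is the first GS-5829 dose. The consequence is confined to the TEAE summaries of the combination groups, where lead-in events may be incomplete and, where present, are not distinguished from events after GS-5829 starts.

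**What to change.** 1. **Protocol 6.4.1.** End the restriction at the first dose of any study drug: Study Day 1 in lead-in cohorts, Cycle 1 Day 1 otherwise. This is one sentence and now serves mainly the record.
2. **SAP 7.1.6.** For combination groups, derive a flag for TEAE onset before, versus on or after, the date of the first GS-5829 dose, and show the two periods separately beside the planned totals.
3. **Data query before database finalization.** Ask sites with combination subjects to check for unrecorded AEs, and review medical-history entries dated between Study Day 1 and Cycle 1 Day 1.

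Items 2 and 3 can still change results. SAP Section 1 places SAP finalization before database finalization and allows later changes to be documented in the CSR. The cost is one derived flag, a few extra tables and a targeted query.
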